## Abstract:

*Background:* Postantibiotic diarrhoea in critically ill patients is common, often protracted and currently there is no effective treatment of it.

*Aim*: To test safety and feasibility of faecal microbial transplantation in critically ill patients with postantibiotic diarhoea.

Design: Prospective, single center, parallel group randomised controlled trial. Subjects: ICU patients (both general and burn ICU) who developed diarhea after a curse of antibiotic therapy that is persistent for 24 hours even after interruption of enteral nutrition. Patients with septic shock or approaching death will be excluded.

Treatment in the intervention group: Faecal bacteriotherapy (FBT) delivered as enema (and repeated once in the subgroup of patients with C. dif. infection) of 350 ml of standardised mixed transplantate prepared from faeces of 7 healthy donors. Control group: Standard-of-care protocolised treatment of postantibiotic diarhea (which includes vancomycine 250 mg p.o. 6 hourly in the subgroup with C. dif. infection).

22.9.2021 Protocol version 9.2

*Primary outcome*: Percentage of patients with treatment failure at day 7 after randomisation, which is defined as treatment either not being delivered or effective. *Secondary and exploratory outcomes*: Influence of the intervention on colonic microbiom and metabolom, small bowel and colonic permeability, bacterial translocation and systemic inflammation.

# **Background:**

Over 80% of critically ill patients receive antibiotic treatment over their ICU stay and it is well documented that it leads in a reduction of the diversity of colonic bacterial flora. In turn, this leads to overgrowth of pathogenic species incl. Clostridium difficile (C.dif.) and multi-drug resistant Enterobacteriaceae and Enterococci. Restoration of physiological bacterial flora is prolonged and a significant proportion of patients suffer from postantibiotic diarrhoea. In particular, postantibiotic diarhea in the critically ill that is associated with C. dif. infection may lead to prolonged ICU stay or complications such as toxic megacolon, sepsis and death. Even non-clostridial postantibiotic diarhoea represent a significant burden to ICU patients and staff, impairing patients dignity and comfort and often increasing their length of stay. Current treatment options are limited as neither prebiotic nor probiotic were found to be consistently efficient in the critically ill and have been found risky in some settings, e.g. pancreatitis. Changes of colonic microbiome are well documented in the critically ill and length and mechanisms of restoration of colonic microbiome are yet unknown. It is also unknown to what extent changes in colonic flora contribute to nosocomial infections by MDR Gram negatives in the critically ill.

In the light of this, restoring physiological bacterial flora in the colon by faecal bacteriotherapy (FBT) could potentially be beneficial. FBT has been shown to be safe and effective not only in the prophylaxis of recurrence after the antibiotic treatment, but also as the first-line treatment in the population of non-critically ill patients with C. dif. infections .

The study will be performed in accordance with the protocol, The Declaration of Helsinki and principles of Good Clinical Practice: Consolidated Guidelines. The protocol is consistent with any applicable local regulations.

## Hypothesis and aims:

We hypothesise that FBT will be feasible as first-line treatment of postantibiotic diarrhoea in the critically ill, incl. those with uncomplicated C. dif. infection.

# Primary end-point:

• Percentage of patients with treatment failure at day 7 after randomisation. Treatment failure is defined as either failure to administer allocated treatment for any reason or the presence of diarrhoea on day 7 after randomisation (as assessed by personnel blinded to treatment allocation).

22.9.2021 Protocol version 9.2

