# Secondary end-points are:

- Composite number of adverse events such as new-onset sepsis, toxic megacolon, positive post FBT blood culture, or other SAE assessed by the physician-in-charge as possibly related to FBT.
- SOFA score at days 4 and 7.
- Percentage of patients that are recurrence-free at time of hospital discharge or day 28, whichever occur earlier.
- Subgroup analysis will be performed for patients who are C. dif. positive vs. negative and those who will receive antibiotics for a new extraabdominal infection vs. those who do not.

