# Assessment of primary outcome:

An independent data analyst will retrospectively review the de-identified printouts of nursing notes from the two 12 hour shift day + night ending in the morning of day 7 and record the presence or absence of diarrhoea (defined as 3 or more stools per day or Bristol type 7 stool in the volume >300 ml/day if stool derivative device is inserted).

In case the patient is not on ICU, but remains at hospital, the research nurse will bring a special record form on day 6 and instruct both the patient and nursing staff to record during the next 24 hours the volume or frequency and consistency of stool using visual Bristol Scale and also to provide a sample of stool. In case the patient has been discharged, he/she will be contacted the day before over the phone by a research nurse and the next day the patient will be asked to bring the formulary and a stool sample to hospital of will be visited by a research staff at home.

Afterwards, as long as the patient remains on ICU, adverse events, antibiotic treatment, and stool volume/frequency are monitored daily.

Unique Protocol ID: 2021-002290-25 22.9.2021 Protocol version 9.2

In patients with faecal management device in place, follow up visits (identical to Day 4) are performed in 7 days interval up to day 28, and/or ICU discharge or FMD removal, whichever occurs earlier.

In patients who remain in ICU, but have had FMD removed, have the same follow up procedures, with the exception of stool sampling. Stool is collected and stored as close as practical to the day of the visit after the patient has had spontaneously defecated.

In patients who are not on ICU, but remain at hospital, will be visited by a research nurse at day 7, 14, 21 and 28 as long as they remain hospitalised. The visit will include monitoring of adverse event, notice on patient general status, the presence/absence of diarrhoea, antibiotic medication. Blood will be collected and frozen. Six month follow up is performed at follow up clinics and it includes history (incl. recent history of diarrhoea), physical exam and blood sampling. Patients willing to do so are requested to bring in a stool sample. Patients unwilling to show up will be interviewed over the phone.

	D0	D1	D2	D3	D4	D 5-6	D7	D14, 21, 28or D/C	6month follow up
ICF	х								
Review drug chart	Х								
Serum sample + freeze	х	x			х		x	x	х
Stool sample + freeze	х				х		х	(x)	х
Adverse events, Phys.exam, SOFA	х	х	х	х	х	х	х	х	
Blood culture		хх							

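### A treated patient with toxic megacolon whose day-7 stool falls below the diarrhoea threshold is scored a primary-endpoint success, although the protocol counts the same event as a harm

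*Combined protocol and SAP*

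**What the plan says.** The Primary end-point section gives two routes to treatment failure: "failure to administer allocated treatment for any reason or the presence of diarrhoea on day 7 after randomisation". The day-7 assessment is to be made by staff blinded to allocation. The Abstract puts the same outcome more loosely, as "treatment either not being delivered or effective", without saying what counts as effective.

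For patients on ICU, the Assessment of primary outcome section gives an independent analyst de-identified nursing notes covering the last two 12-hour shifts up to the day-7 morning. The analyst's task is to "record the presence or absence of diarrhoea (defined as 3 or more stools per day or Bristol type 7 stool in the volume >300 ml/day". The volume criterion applies when a stool device is in place. Patients who have left ICU are assessed from a 24-hour stool record.

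Toxic megacolon appears elsewhere as a harm:
- The Background says that diarrhoea with *C. difficile* infection "may lead to prolonged ICU stay or complications such as toxic megacolon, sepsis and death".
- The first secondary end-point is a "Composite number of adverse events such as new-onset sepsis, toxic megacolon, positive post FBT blood culture" and other events.
- The exclusion criteria remove patients with a colon wider than 9 cm on plain X-ray, and the Day 0 procedures require an abdominal X-ray to rule out megacolon.

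The Statistical plan compares arms on not being cured and has no rule for complications.

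**The concern.** The primary endpoint treats absence of diarrhoea as treatment success, whatever the reason for the absence. If toxic megacolon leaves a patient passing little or no stool, the stool record on day 7 looks the same as a recovery. That patient would appear in the safety composite as a harm and in the primary analysis as a success.

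This is more than a missing detail. The scoring rule is explicit and, applied as written, gives an answer at odds with the Abstract's intention that ineffective treatment is a failure. The assessor is asked only whether diarrhoea is present, so no step in the procedure would catch the case. With 18 patients per arm, a single misplaced patient is visible in the result.

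**Working it through.** **Step 1: apply the rule as written.** Take three patients, all given their allocated treatment, on day 7.

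| Patient | Day-7 stool record | Primary endpoint | Safety composite |
|---|---|---|---|
| (a) recovered | one formed stool | success | no event |
| (b) still ill | four loose stools | failure | no event |
| (c) toxic megacolon since day 5 | no stool | success | event |

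The scores for (a) and (b) are as intended. Patient (c) was treated, so the first route to failure is closed. There are fewer than three stools and no qualifying volume, so the second is closed too. Neither the Statistical plan nor the Monitoring of safety section changes that score. A megacolon patient who still meets the stool definition is already a failure, so the gap concerns only those below the threshold.

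**Step 2: reproduce the plan's sample size.** Inputs from the sample size section: success 45% on control and 66% on faecal bacteriotherapy (FBT), margin 20 points, one-sided 5%, power 80%, 1:1 allocation. With unpooled variances:

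n per arm = (z₀.₉₅ + z₀.₈₀)² × [p_C(1 − p_C) + p_T(1 − p_T)] / (p_T − p_C + margin)²
= 6.183 × (0.2475 + 0.2244) / 0.41²
= 17.4, rounded up to 18.

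That is 36 in total, as stated.

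**Step 3: weight of one patient.** 1/18 = 5.6 percentage points of an arm's failure rate. Relative to the margin, 5.6/20 = 28%.

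**Step 4: illustration of sensitivity.** Assume that the planning rates already contain one such patient as a success and that this patient is recoded as a failure. Power = Φ[(0.20 + p_T − p_C)/SE − 1.645], where SE = √{[p_C(1 − p_C) + p_T(1 − p_T)]/18}.

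| Recoded | p_C | p_T | SE | Power |
|---|---|---|---|---|
| none | 0.450 | 0.660 | 0.162 | 81% |
| one in the FBT arm | 0.450 | 0.604 | 0.164 | 70% |
| one in the control arm | 0.394 | 0.660 | 0.160 | 90% |
| one in each arm | 0.394 | 0.604 | 0.163 | 81% |

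The shift is about 10 points of power either way, depending on the arm, and is negligible if the events balance. The table shows leverage. It does not forecast how often the event will occur.

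**The case against.** **The harm is captured elsewhere.** Toxic megacolon is a named component of the secondary safety composite. Adverse events are recorded daily to day 7, treating clinicians can raise concerns, and safety is reported by intention to treat. Keeping symptom response and harm in separate endpoints is a legitimate design. This stands as a reason not to call the trial unsafe or the harm hidden. It does not correct the primary failure rate, in which the patient remains a success.

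**The case depends on stool falling below the threshold.** No section says that toxic megacolon stops stool. This stands, and it is why the point is confined to patients below the threshold.

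**Likelihood.** A reader might assume that 2% to 5% of patients are affected and infer a chance of at least one misclassified patient of 1 − 0.98³⁶ = 52% to 1 − 0.95³⁶ = 84%. The documents do not support this:
- They give no rate.
- The Background ties the complication to *C. difficile* infection, a subset of unstated size, whereas the calculation uses all 36 patients.
- It gives the chance of any megacolon. Misclassification also requires treatment given, onset by day 7 and stool below the threshold, so the range is at most an upper bound under an assumed rate.
- Entry screening for colon diameter, lactate and sepsis may lower the risk further, by an unknown amount.

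**Direction.** A reader might also infer that the rule favours FBT. Bowel-directed care does differ between arms, so equal event rates cannot be assumed, but nothing in the documents shows which arm would have more events.

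**A wider gap.** The primary endpoint is equally silent on death before day 7 and on rescue intravenous antibiotics. That is correct, and this fix does not settle those cases. It is no reason to leave this one mis-scored.

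**Conclusion.** The point holds in limited form. Under the stated rule, a treated patient with toxic megacolon and stool below the diarrhoea threshold on day 7 is a primary-endpoint success and, at the same time, a harm in the secondary composite. This follows from the text and needs no assumed rate.

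The size per event is 5.6 percentage points of an arm's failure rate, assuming 18 analysed per arm. How often it would occur is unknown and may be rarely or never in 36 patients. The direction between arms is also unknown. The power figures of 70% and 90% rest on the plan's 45% and 66% and on exactly one affected patient in one arm. The change is worth making before any data are seen, because it is cheap and a later decision on a single patient could look driven by the result.

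**What to change.** Add to the Primary end-point section: *A patient with toxic megacolon recorded as an adverse event between randomisation and day 7 is a treatment failure, whatever the day-7 stool record.*

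Add to the Assessment of primary outcome section: *This rule is applied after the blinded stool reading has been completed. The independent analyst confirms the event from de-identified records. The result based on the stool record alone is reported as a sensitivity analysis.*

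Cost: one sentence in the first section and a short paragraph in the second. Adverse events are already recorded through day 7, and neither the sample size nor patient management changes. There are two downsides. The failure rate may be slightly higher. The endpoint would also depend in part on events first recorded by clinicians who know the allocation, and the only scheduled abdominal X-ray is on Day 0, so recognition could differ between arms. Confirmation from de-identified records and the stool-only sensitivity analysis limit that risk but do not remove it.

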# Secondary end-points are:

- Composite number of adverse events such as new-onset sepsis, toxic megacolon, positive post FBT blood culture, or other SAE assessed by the physician-in-charge as possibly related to FBT.
- SOFA score at days 4 and 7.
- Percentage of patients that are recurrence-free at time of hospital discharge or day 28, whichever occur earlier.
- Subgroup analysis will be performed for patients who are C. dif. positive vs. negative and those who will receive antibiotics for a new extraabdominal infection vs. those who do not.

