## Study subjects:

- Inclusion Criteria: All of the following: Informed consent (see below), Age > 18 yrs., In-patient in ICU or HDU (incl. burn unit) and expected to stay for >7 days, Diarrhoea following antibiotic treatment defined as 3 or more stools per day or Bristol type 7 stool in the volume >300 ml/day if stool derivative device is in place, persisting for 24 hours despite enteral feeding formula has been stopped.
- Exclusion criteria: Death appears imminent or ceilings of care put in place, presence of new-onset sepsis defined as per 2016 definition, lactate >2.0 mM, colon diameter > 9 cm on plain AXR, the necessity of ongoing antibiotic treatment for another reasons. Unable to tolerate enema for any reason (e.g. surgery of the GI tract in the past year). Pregnant and lactating woman. Patients with a history of severe anaphylactic food allergy, any other reason

22.9.2021 Protocol version 9.2

which — as per judgement of the treating clinician — makes faecal transplantation unsafe or not feasible (Note: All screening failures based on this criterion will be reported separately, inc. the reason why it was considered unsafe or not feasible to proceed).

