# Intervention group :

- if considered safe, the patient receive Loperamide 2 mg p.o. 2 hours before FBT.
- FBT procedure 350 ml of thawed donor stool (stool suspension) will be delivered by retention enema in the patients colon. The patient will be positioned in left semilateral Trendelenburg's position for 15 minutes and then in right semilateral Trendelenburg's position for another 15 minutes. Faecal management system (e.g. FlexiSeal©) will be inserted and clamped for 2hours after FBT
- in all patients receiving FBT will be recorded body temperature, heart rate, oxygen saturation and blood pressure. 3hours after FBT blood culture will be taken.

- in the subset of patients with C. dif. positivity, 1 L normal saline enema will be performed at the time of CDI diagnosis and FBT will be repeated once more. No antibiotics will be administered (with rescue option of administration of i.v. tigecycline).

**FBT stool suspension** will be stored in specific –80°C freezer with connected alarm notification to guarantee continuous registration of the storage. Information on the FBT suspension labels includes donor code, suspension number, production and expiration date, volume, and storage temperature instruction. From each donor one of the sample will be store in freezer for the duration of the ongoing study.

The resulting faecal bacteriotherapy (FBT) preparation is defined as a mixture of 7 aliquots of processed stool intermediates from 7 donors.

The resulting graft will be drawn into four sterile 100 ml syringes and transferred to the ward where the recipient is hospitalized. Re-freezing of thawed or partially thawed extract is not permitted.

# Day 2, 3

Physical examination, SOFA score, evaluation of laboratory blood results (WBC, CRP, lactate, etc.) will be recorded as well as volume or frequency and consistency (Bristol scale) of stool. Concomitant medication and adverse events will be recorded.

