# Monitoring of safety:

Although it is potentially beneficial and has been safely performed in ICU patients, there are only limited data about FBT safety in patients with potentially disrupted intestinal barrier. In turn, following measures have been taken to maximise safety of the current study for patients:

- Treating clinician will not be blinded to treatment allocation and they will be encouraged to speak up should any safety concerns arise.
- Before and 3 hours after FMT, vital signs, blood cultures, endotoxin and early cytokine levels will be measures to specifically look at potential bacterial translocation.
- All patients' vital functions will be continually monitored as per local standards. Frequency, volume and character (as per Bristol scale) of stools will be recorded in 12 hour intervals.
- Onset of sepsis or elevation lactate > 2mM or the presence of pyrexia >38 C with >30% rise of inflammatory markers without clear alternative reason (e.g. HAP) will trigger, in both groups, the addition of intravenous tigecycline or intravenous vancomycine, if C. dif positivity is known or suspected.
- I.v. antibiotics efficient against C. dif. can be added in both groups if a treating clinician considers this appropriate. Reason for doing so will be recorded.
- Should a SUSAR appear, it will be reported as per local legislature and within 48 hours reviewed by the team of investigators, together with independent safety advisors (prof. [name]. Dept. of Infectious Diseases, Na Bulovce Hospital, Prague and Dr.[name], REB Chair FNKV Univ. Hospital), a representative of nursing staff independent on the study. Two SUSARs in the intervention group would automatically lead to termination of the trial for safety reasons.

Unique Protocol ID: 2021-002290-25 22.9.2021 Protocol version 9.2

In addition, the same team will meet ad hoc whenever safety concerns arise. The
team will review data collected from first 8 subjects who have been randomised and
focus on the analysis of adverse events. In particular, the team will review the dynamics of body temperature, heart rate, blood pressure, lactate and blood cultures
before and after FMT. The decision will be taken to continue or terminate the study.

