# Statistical plan:

Safety parameters will be reported on intention-to-treat basis. Primary outcome will be compared by as unadjusted hazard ratio of not being cured (with 95% interval) in a per protocol analysis. The subset of patients with C. dif positivity will be analysed separately.

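### The safety composite counts events from overlapping components without a counting rule, and the overlap falls almost entirely in the FBT arm, so reported totals can mislead with 18 patients per arm

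*Combined protocol and SAP*

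**What the plan says.** All references are to the combined protocol and SAP.

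- **Secondary end-points.** The first item is a "Composite number of adverse events such as new-onset sepsis, toxic megacolon, positive post FBT blood culture, or other SAE", with the qualifier "assessed by the physician-in-charge as possibly related to FBT". By contrast, the primary end-point and the recurrence end-point are both percentages of patients.
- **Intervention group.** For patients who receive FBT, "3hours after FBT blood culture will be taken". The control group section has no counterpart.
- **Monitoring of safety.** "Before and 3 hours after FMT, vital signs, blood cultures, endotoxin and early cytokine levels will be measures", to look for bacterial translocation. The same section states: "Treating clinician will not be blinded to treatment allocation".
- **Study subjects.** A sepsis definition appears only as an exclusion criterion: "presence of new-onset sepsis defined as per 2016 definition".
- **Statistical plan.** "Safety parameters will be reported on intention-to-treat basis". No counting unit, hierarchy of components, comparison or test is given for safety.
- **Schedule table.** Adverse events are marked in every column from D0 to D7 and again in the column for days 14, 21, 28 or discharge.

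**The concern.** The sample size section names feasibility and safety as the purpose of the pilot, so readers will look closely at the safety totals. Three features make those totals hard to read.

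1. **No counting rule.** Blood cultures are taken to detect translocation, which is also a route to sepsis, so a joint sepsis and positive culture is foreseeable. Two analysts could report different totals from the same records.
2. **Unequal opportunity to score.** A control patient cannot have a post-FBT culture and can hardly have an SAE related to FBT. The same illness can therefore score higher in the FBT arm.
3. **No window in the definition.** The schedule bounds the collection of events, but the end-point does not say over which period they are counted.

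At stake is whether the published comparison reflects how many patients were harmed, or how many labels each patient collected.

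**Working it through.** **1. The plan's own figure.** The plan gives no expected rate, size or power for the safety composite. Its only size is 36 patients, from the non-inferiority calculation (control success 45%, FBT 66%, margin 20 points, one-sided 5%, power 80%):

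n per arm = (1.645 + 0.842)² × (0.45×0.55 + 0.66×0.34) / (0.66 − 0.45 + 0.20)² = 6.18 × 0.4719 / 0.1681 = 17.4, rounded up to 18.

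This reproduces 36 in total. The checks below use 18 per arm.

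**2. What one episode scores under the literal wording**

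| Clinical picture | FBT arm | Control arm |
|---|---|---|
| Sepsis alone | 1 | 1 |
| Sepsis with bacteraemia found by culture | 2 (if it is the post-FBT culture) | 1 |
| The same, with toxic megacolon | 3 | 2 |

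The SAE item is introduced by the word 'other', so it does not naturally recount the same sepsis.

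**3. Effect on reported totals.** Assume that every affected FBT patient scores twice and every affected control once. This is the extreme case.

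- 3 versus 3 patients (16.7% in each arm, risk difference 0): 3×2 = 6 versus 3×1 = 3 events. An apparent two-fold excess appears where there is none.
- 3 FBT versus 6 control patients (16.7% versus 33.3%, difference −16.7 points): 3×2 = 6 versus 6×1 = 6 events. The difference disappears.

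**4. If someone tested the totals.** The plan specifies no such test, so this is illustration only. Treating events as independent, an exact binomial test of 6 versus 3 gives p = 0.51. Fisher's test on 3 versus 3 patients gives p = 1.0.

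The table shows false-positive rates at a nominal 5% with no true difference. They were enumerated exactly with affected patients ~ Binomial(18, p) in each arm. Both p = 20–40% and the share of episodes counted twice are assumptions.

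| Share of episodes counted twice | Both arms | FBT arm only |
|---|---|---|
| None | 0.5–0.8% | 0.5–0.8% |
| 25% | 2.2–3.1% | 2.2–2.4% |
| 50% | 3.7–5.5% | 4.9–6.7% |
| All | 4.8–9.2% | 14.9–24.2% |

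Fisher's test on patients with at least one event stays at 2.1–2.6% over the same range. The result depends on the assumed overlap, and marked inflation needs nearly all FBT-arm episodes to be doubled.

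**The case against.** **The end-point is merely under-specified; the plan never says components are summed.** This is correct as far as it goes. The rule is absent, so an episode can count twice, not that it does. But the stated unit is a number of events, and the same document uses percentages of patients where it wants them, so the literal reading is a fair one.

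**No test is planned.** This stands. A reader might infer an inflated type I error. If episodes score one to three events in both arms, with 50–80% scoring two or three, testing totals as independent counts gives roughly 7–13% false positives. Nothing in the documents supports that overlap or that test. A rank or permutation test on per-patient counts would also respect the clustering.

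**A routine triple count.** A reader might count bacteraemic sepsis a third time as an SAE. The wording excludes this; a third count needs another listed event such as toxic megacolon.

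**Longer ICU stay raises the count.** A reader might infer this from "as long as the patient remains on ICU, adverse events, antibiotic treatment, and stool volume/frequency are monitored daily", set against weekly ward visits. That sentence follows the day-7 assessment. Up to day 7 the schedule marks adverse events in every column. After that, a weekly visit that asks about adverse events does not imply that sepsis or an SAE is missed.

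**Control patients may also be cultured.** The schedule table marks blood cultures on D1 without naming an arm. However, the text ties them to the time before and 3 hours after FBT, and a control culture would still not be a post-FBT culture.

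**The weight is limited.** This is one secondary end-point in a feasibility trial, and a team with independent advisors reviews adverse events. That limits the consequences but does not settle what the reported number means.

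**Conclusion.** The point holds as a defect of definition. The composite is an event count with an open list of components that can overlap, and it has neither a rule for shared episodes nor a stated window. A double count is supported by the wording and arises essentially in the FBT arm. The SAE component adds a further asymmetry, because relation to FBT is judged by the physician in charge and treating clinicians are unblinded.

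In the extreme case where every affected FBT patient is double-counted, equal harm (3 versus 3 patients) reads as 6 versus 3, and half the harm (3 versus 6) reads as 6 versus 6. The real distortion depends on how often sepsis coincides with a positive post-FBT culture, for which the documents give no figure. The documents do not support a claim about a controlled error rate or about length of ICU stay. The change is worth making before the data are analysed; it does not threaten the primary end-point.

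**What to change.** Replace the first secondary end-point with: *number and percentage of patients with at least one of new-onset sepsis, toxic megacolon or any SAE, regardless of judged relation to FBT, from randomisation to day 7 and from randomisation to day 28 or discharge*. Then add to the statistical plan:

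- The arms are compared by risk difference with an exact interval, by intention to treat as already stated.
- One clinical episode is counted once. Components are tabulated separately by arm and not summed.
- Positive post-FBT blood cultures and SAEs judged possibly related to FBT are described for the FBT arm only, outside the between-arm composite.
- The sepsis definition for the end-point is stated; at present one is given only for exclusion.

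Keeping the present components and merely switching to patients with at least one event would not be enough, because the FBT-only components would still load one arm.

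**Cost.** No extra patients or measurements are needed. Repeat events in one patient would appear only in a listing. Including any SAE broadens the composite, which is why the component table matters. Since a protocol end-point changes, an amendment notified to the ethics committee is required.
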